2.2 Sample Size Determination

In the UK Phase 2 study of patients with Gorlin syndrome (Pelle-926-201), the mean number of nSEBs (erroneously stated in the protocol as mean number of new BCCs in the Section on Sample size determinations) at 6 months was █ in the Patidegib Topical Gel, 2%, group with an SD of █, and a mean of 1.4 in the Vehicle Gel group with a SD of 1.52. The effect size was 0.81. Because the current trial is longer, more conservative assumptions are made. It is assumed that at 6 months, the mean number of nSEBs in the Patidegib Topical Gel, 2%, group will be 0.6, with an SD of █, while at 6 months the mean and SD in the Vehicle Gel group will be the same as in the Phase 2 study at 6 months for an effect size of 0.63. At 12 months, it is assumed that the means and SDs will be twice those of 6 months. With these assumptions, █ subjects in the Patidegib Topical Gel, 2%, group and 63 in the Vehicle Gel group (for a total of █ subjects) will give >90% power for a 2-sided 0.05 level statistical significance. To account for a 16% drop-out rate, approximately 150 subjects will be randomized.

The primary endpoint of number of qualifying nSEBs per subject by Month 12 may be affected by follow-up time. Based on the UK Phase 2 study (Pelle-926-201), it is projected that the power calculated above will be substantially similar unless marked differences are seen between the treatment arms in follow-up time. Sample size was calculated based on a Wilcoxon-Mann-Whitney test which is conservative if the underlying distribution is Negative Binomial.

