The Negative Binomial regression was selected as the primary method of analysis to account for the potential for overdispersion. Using the Negative Binomial model, the power will be somewhat higher than the one calculated using a non-parametric Wilcoxon-Mann-Whitney test. The proposed sensitivity analysis, Rank ANCOVA, was selected to corroborate the results from the Negative Binomial model. If the distribution is markedly different from Negative Binomial (and unknown to sufficiently allow a different parametric regression model), then the non-parametric ANCOVA gives type-1 error closer to the nominal level.

Analysis	ITT		PP	
	Negative Binomial	Rank	Negative Binomial	Rank
MI	x; s	x; s		
LOCF	x	x		
OC	x	x	x; s	x; s
Derived	Listing Only			

Note: 'x' denotes that the full population will be used, and 's' denotes that subgroup analyses will be provided in the given population and analysis type.

The primary method for dealing with missing data will be the multiple imputation (MI) method discussed in detail in [Section 3.2](#). An analysis in the PP Population using the observed case (OC) method with the offset option specified to account for different follow-up times will be provided as a sensitivity analysis. A box plot of the mean number of nSEBs per subject over time will be presented. Additionally, a stacked histogram showing the proportion of subjects with 0, 1, 2, 3, 4, and █ nSEBs will be presented over time in the ITT Population.

Last Observation Carried Forward (LOCF) and OC analyses using both the Negative Binomial and Rank ANCOVA models will be done as sensitivity analyses. Additional sensitivity analyses (conservative multiple imputations and tipping point analysis) are described in [Section 3.2](#).

The derived number of nSEBs, determined using the actual measurements provided instead of relying on the answer to the question "Lesion has a longest diameter █ mm and has grown by at least █ mm in longest diameter from Baseline:", will be presented in the listings. If the post-baseline measurement is missing which makes the derivation impossible and the baseline measurement is present, then the question will be used instead to determine if the BCC qualifies as a nSEB. However, if there is no baseline measurement, then the lesion will not count as a nSEB.

Pelle-926-301 Statistical Analysis Plan

17 June 2020

Listings of derived efficacy endpoints, BCC measurements, facial BCC procedures, and digital imaging of BCCs will be created.

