3.2 Missing Data

For the primary analysis, the MI method will be the primary method for dealing with missing data. LOCF and OC analyses will be done as sensitivity analyses. For the count secondary endpoints, MI will be used; for the dichotomous secondary endpoints and the aBCCdex endpoint, LOCF will be used.

For the MI model, 100 imputations will be generated using PROC MI of SAS. Fully conditional specification (FCS) model using the regression method will be used with the change from the last time-point in the number of SEBs at prior post-baseline visits, number of BCCs that are not SEBs at baseline, prior HHI therapy, gender, geographic region, and age ██████████ as covariates to impute any missing data including missed visits and missing data due to dropouts. Missing data of subjects on Patidegib who discontinued due to intercurrent events of AEs, use of a prohibited concomitant medication or lack of efficacy (determined during blind data review of the reasons for study treatment stopped) will be imputed based on vehicle and imputed based on randomized treatment for remaining subjects to estimate the treatment effect if patients would continue to be treated for the entire study unless forced to discontinue treatment due to an AE or lack of efficacy or used a prohibited concomitant medication. If there is a problem with imputing based on the full model, then region will be dropped. The ROUND and MINIMUM options will be utilized to ensure imputed values are non-negative integers. The seed to be used is 20180330. The results from the MI will then be used to derive the number of nSEBs at each timepoint and then analyzed using the primary analysis model. The results of the 100 analyses will be transformed into a normal statistic and combined into a single analysis using

Pelle-926-301 Statistical Analysis Plan

17 June 2020

PROC MIANALYZE. The Wilson-Hilferty transformation (Wilson and Hilferty, 1931) will be utilized to combine the results of the 100 non-parametric Rank ANCOVA analyses.

For the primary and secondary efficacy endpoints related to number of nSEBs, a nSEB that was first reported at or prior to Month 12 will be counted in the endpoint. The lesion will be considered a nSEB at the time it was first reported clinically even if it is biopsied and confirmed later.

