The following additional sensitivity analyses utilizing Negative Binomial regression will be provided for the primary endpoint to explore the space of plausible missing data assumptions:

- An MI analysis using the model for the primary imputation but by vehicle for all subjects who dropped out, irrespective of the cause, and MI by randomized treatment for the remaining subjects.
- A tipping point analysis which will impute the results at the months prior to the analysis using the same model for the primary imputation will be performed if and only if the result of the primary endpoint is significant. One hundred imputations will be generated using PROC MI of SAS. The imputation at Month 12 will be imputed using the MNAR ADJUST statement within SAS to shift the imputed values for the increase in nSEBs for subjects randomized to the Patidegib arm by different values until the p-value changes from significant to non-significant. The seed to be used is 20180330.

In order to classify a medication as prior or concomitant or classify an AE as treatment-emergent or not, missing or partial dates will be imputed. Please see Appendix D for full details of the imputation of missing/partial dates.

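### The primary multiple imputation draws sparse lesion increments from a normal model and forces them to non-negative integers, biasing imputed counts upward; for nSEBs this moves the rate ratio toward 1 by about 1–7% and leaves power essentially unchanged

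*SAP*

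**What the plan says.** SAP section 3.2 makes multiple imputation the main method for missing data, with 100 imputations from PROC MI. The model is: "Fully conditional specification (FCS) model using the regression method will be used with the change from the last time-point in the number of SEBs", together with baseline lesion count, prior HHI therapy, gender, region and age. Then: "The ROUND and MINIMUM options will be utilized to ensure imputed values are non-negative integers".

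The change since the last visit is listed among the covariates. That the increment is also the imputed variable is a reading. It is supported by the same section, which derives nSEB counts at each timepoint from the imputed results and describes the tipping-point analysis as one that will "shift the imputed values for the increase in nSEBs for subjects randomized to the Patidegib arm".

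Missing data of patidegib subjects who stop for an adverse event, a prohibited medication or lack of efficacy "will be imputed based on vehicle and imputed based on randomized treatment for remaining subjects". A sensitivity analysis reuses the model but imputes "by vehicle for all subjects who dropped out, irrespective of the cause".

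Protocol section 12.7.6 also plans FCS imputation, for new BCCs or nSEBs. It leaves the details to the SAP and names neither ROUND nor MINIMUM. The SAP (June 2020) treats nSEBs as primary; protocol section 12.6.1.1 makes new BCCs primary.

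**The concern.** The FCS regression method draws from a normal distribution. When the mean increment is well below one lesion and the spread exceeds the mean, many draws are negative. Whether negatives are redrawn or raised to zero, the mean of what remains is higher than the mean the model estimated. The inflation is proportionally larger in the arm with fewer lesions, so at equal dropout the ratio of patidegib to vehicle is pulled toward 1.

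What is at stake is an avoidable bias in the SAP's main estimate. No planned analysis isolates it: the vehicle-based MI and the tipping-point analysis reuse the same imputation model, while LOCF and observed-case analyses change the missing-data assumption as well.

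**Working it through.** **Inputs.** At 6 months: vehicle mean 1.4, SD 1.52; patidegib mean 0.6 (SAP 2.2), SD 0.94 (protocol synopsis). "At 12 months, it is assumed that the means and SDs will be twice those of 6 months": so 2.8 (SD 3.04) and 1.2 (SD 1.88). "To account for a 16% drop-out rate, approximately 150 subjects will be randomized", taken as 75 per arm.

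**The plan's own figures reproduce.** Effect size: 0.8/√((1.52² + 0.94²)/2) = 0.633, stated as 0.63. With 63 per arm a two-sample comparison has 94.4% power, or 91.0% at a Wilcoxon efficiency of 0.864, consistent with the stated >90%. 126/0.84 = 150. The documents give no figure for imputation bias.

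**Share of negative draws.** Four quarterly assessments are assumed; the SAP's visit windows are blacked out.
- Mean per quarter: 2.8/4 = 0.70 and 1.2/4 = 0.30.
- Negative binomial dispersion from the 12-month SDs: (3.04² − 2.8)/2.8² = 0.82 and (1.88² − 1.2)/1.2² = 1.62.
- Quarterly SD: √(0.70 + 0.82 × 0.70²) = 1.05 and √(0.30 + 1.62 × 0.30²) = 0.67.
- Normal probability below zero: Φ(−0.70/1.05) = 25% and Φ(−0.30/0.67) = 33%.
- Within simulated MI, conditional on prior quarters: 20–26% (vehicle) and 31–33% (patidegib).

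**Imputed means.** The SAP does not say how MINIMUM treats negative draws, so three readings were run: redraw below zero then round; round then redraw negatives; set negatives to zero. The mean imputed quarter rises from 0.70 to 0.76–1.12 (vehicle) and from 0.30 to 0.35–0.60 (patidegib).

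**Hand check.** If 16% leave after quarter 1, 2 or 3 with equal chance, each misses 2 quarters on average, or 0.16 × 2 = 0.32 imputed quarters per randomized subject.
- Vehicle mean rises by 0.32 × (0.06 to 0.42)/2.8 = 0.7% to 4.8%.
- Patidegib mean rises by 0.32 × (0.05 to 0.30)/1.2 = 1.3% to 8.0%.
- Rate ratio: 1.013/1.007 to 1.080/1.048, about +0.6% to +3.1%.

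**Simulation.** 75 per arm, four quarters, random dropout, sequential Bayesian regression on prior quarters within arm, fewer imputations than the planned 100 (20 in the main runs). Shifts are against the same regression without ROUND or MINIMUM. Where dropouts are imputed by arm, those unconstrained draws recover the full-data ratio (0.416 against 0.416 in one set of runs). So the constraint is the cause.

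| 16% dropout in both arms | Rate ratio shift |
|---|---|
| All imputed by arm, none leave before Month 3 | +1.2% to +3.1% |
| All by arm, some leave before Month 3 | +2.0% to +4.3% |
| Half of patidegib dropouts from vehicle | +2.4% to +5.6% |
| Both of the last two | +2.9% to +6.7% |

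A constant lesion rate cannot match the 6- and 12-month SDs together. A model that closely matches both gives +0.8% to +2.0% for the first row. Runs that include it put the low ends of the next two rows at 1.2% and 1.3%. In the all-from-vehicle sensitivity MI the shift is +1.7% to +7.7%.

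Baseline covariates were left out of these runs. A check with a strongly predictive baseline count, imputed by arm and compared with complete data, gave +1.2% to +4.2%.

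**Effect on inference.** The SE of the log rate ratio is 0.17–0.21. The by-arm shift is 0.04–0.17 SE. Even +6.7% is ln 1.067 = 0.065, roughly 0.3–0.4 of such an SE. Power by arm is 0.978–0.979 against 0.978 with predictive mean matching; runs that include early leavers gave 97.4–98.6% against 97.8% unconstrained. Power was not run with vehicle-based imputation. With no true effect and equal dropout, one-sided false positives are 2.7–3.3% against 2.9–3.0% with predictive mean matching (Monte Carlo error about 0.3 point).

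**The case against.** The strongest reply is that this changes no decision. Under planned dropout the shift is a fraction of a standard error, it works against patidegib, and power and false positives barely move. That stands, and it is why the point is minor.

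A second reply is that the plan already has protection: "Last Observation Carried Forward (LOCF) and OC analyses using both the Negative Binomial and Rank ANCOVA models will be done as sensitivity analyses", neither of which uses normal draws, and the tipping-point analysis penalises patidegib's imputed increments whenever the primary result is significant. This stands in part. The tipping-point analysis does guard against a bias in patidegib's favour, but because it starts from the same imputed values it cannot show how much of the estimate comes from the constraint.

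Two stronger readings are tempting. A reader might infer that the constraint favours patidegib and inflates false positives. That needs an imbalance found in neither document. At an assumed 24% vehicle and 8% patidegib dropout, with the planned effect, the shift is −0.3% to −3.0%. With no true effect (12-month mean 2.8 in both arms) false positives are 2.9–5.3% against 2.6% with predictive mean matching, but only 2.9–3.3% when both planning SDs are matched. At a lower common mean of 1.2 they are 2.2–7.4% against 1.8–2.7%. At 20% and 12%, with the planned effect, the shift is about nil (−0.4% to +0.7%).

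Conversely, a reader might call the step conservative by construction. It is not: the direction depends on how much is imputed in each arm.

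Finally, predictive mean matching is not exact. It leaves 0.5% or less by arm at the planning rates and +0.4% to +1.3% with vehicle donors, which touches the low end of the bias it replaces.

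**Conclusion.** The point holds as a small, avoidable bias. For nSEBs at 16% dropout in both arms, the rate ratio moves toward 1 by about 1–3% when all dropouts are imputed by arm after Month 3. It moves by about 2–7% with earlier dropout, with half of the patidegib dropouts imputed from vehicle, or with both; the lower end nears 1% if both planning SDs are matched. Power is essentially unchanged.

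This rests on the increment being the imputed variable, four quarterly assessments, and the assumed dropout timing and vehicle-imputed share. How MINIMUM treats negative draws accounts for much of each range.

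These sizes should not be carried over to new BCCs, for which the documents give no rate. Purely as an illustration, assumed rates of 0.5 to 3 times the nSEB rate with a similar coefficient of variation give −0.5% to +2.9% by arm at equal dropout, so even the sign is not certain there.

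**What to change.** In SAP section 3.2, replace the regression method with ROUND and MINIMUM by FCS predictive mean matching, or by a count-based imputation. Apply it to the increment in the endpoint being analysed: new BCCs, and nSEBs separately. Name that increment explicitly as the imputed variable. Use vehicle donors wherever vehicle-based imputation applies.

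Use the same model in the vehicle-based sensitivity MI. Restate how the tipping-point shift is applied to it, for example as whole-lesion shifts or as a multiplier on the rate.

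The cost is SAP wording and minor reprogramming of the imputation and tipping-point steps, with no extra data. Predictive mean matching brings fewer distinct donors in a small arm and a residual bias of about 1% or less in most runs.

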3.3 Pooling of Sites

Approximately █ centers are planned in this study in 2 geographic regions: North America (USA and Canada), and Europe. ANCOVA analyses of primary and secondary endpoints will include geographic region, in addition to other factors, as a covariate. Sub-group analyses of primary efficacy endpoints will be done by geographic region in addition to other stratification factors age █, gender, and prior HHI therapy if at least 30 subjects are in a subgroup.

3.4 Protocol Deviations

Protocol deviations and violations will be monitored. Before unblinding the study, protocol deviations will be classified as minor, or those major deviations that may impact on the interpretation of the results. Major protocol deviations in regard to inclusion/exclusion criteria, prohibited concomitant medications, or treatment compliance not between 80% – 120% will cause the removal of subjects from the PP population. A summary of deviations by impact (major vs. minor) and COVID-19 related deviations will be summarized in the ITT Population. All deviations will be provided in a listing. Additionally, a listing of missed visits due to COVID-19 will be presented.

3.5 Compliance with Study Drug Application

At each visit when study drug is returned by the subject, returned tubes will be weighed. Compliance with study drug application will be calculated from the previous dispensation of study drug. Compliance will be calculated using the following formula:

[REDACTED]

Where DW represents the dispensed weights and RW represents the returned weights of each kit. If a tube is not returned, then it will be assumed that the subject used none of it, i.e. the returned weight equals the dispensed weight. An alternative compliance calculation based on the following formula:

[REDACTED]

will be presented.

Total dose received, duration of treatment, and compliance will be compared between the 2 treatment groups using summary statistics. Compliance will also be a factor in defining the PP population as noted in Section 2.3.

Listings of baseline study drug application, study drug accountability, compliance, and study drug interruption will be created.

Compliance will also be calculated based on the cumulative number of days that study drug was interrupted. If drug is interrupted for one day it will be assumed that two doses were missed which will be a conservative estimate of the number of doses missed.

4. CHANGES FROM THE PROTOCOL

This section highlights text in the SAP that overrides the cited text in the protocol.

The protocol (Section 8.2.1) refers to an Imaging Review Charter. In actuality this is an Imaging Review Work Instruction.

In the section on Sample Size Determination (Section 12.9) the protocol states ‘mean number of new **BCC** lesions at 6 months was 0.42’ instead of ‘mean number of new **SEB** lesions at...’

The secondary endpoints for the number of nSEBs at Months 6 and 9 were clarified to reflect that they are “by Month” 6 or 9 to bring these endpoints in line with the primary endpoint. Exploratory endpoints for the time to first nSEB, Skindex-16, DLQI, and EQ-5D-5L questionnaires were added.

The primary endpoint analysis distributional assumption was changed from Poisson to Negative Binomial based on FDA and EMA feedback, however the primary endpoint remains unchanged.

Pelle-926-301 Statistical Analysis Plan

17 June 2020

The interim analysis will no longer be performed based on EMA Scientific Advice, dated 26Mar2020, and FDA advice during a Type B Meeting held on 11May2020 recommending that the interim analysis should not be conducted; only a final analysis will be performed at an alpha level of 0.05 instead of 0.045 (both primary and secondary endpoints).

Laboratory test results will be summarized as change from baseline to last result on treatment instead of at each visit to provide a more concise, medically relevant summary.

APPENDIX A: ABCCDEX SCORING

Items answered as not relevant will be scored as '0' for the purposes of scoring.

APPENDIX B: SKINDEX-16 SCORING

A scale will be set to missing if >25% of the items in the scale were left blank. Individual missing items will not be imputed.

APPENDIX C: DLQI SCORING

The scoring of each question is as follows:

Answer	Score
[REDACTED]	1
[REDACTED]	3

The total score is calculated by summing each question's score with a score ranging from 0 to 30. The higher the score, the more impairment in quality of life.

APPENDIX D: PRESENTATION OF DATA AND PROGRAMMING SPECIFICATIONS

General

- Specialized text styles, such as bold, italics, borders, and shading will not be used in tables, figures, and data listings unless they add significant value to the table, figure, or data listing.
- Only standard keyboard characters are to be used in tables and data listings.
- Special characters, such as nonprintable control characters, printer-specific, or font-specific characters, will not be used on a table, figure, or data listing.
- Hexadecimal character representations are allowed (eg, μ , α , β).
- All footnotes will be left justified and at the bottom of a page. Footnotes must be used sparingly and must add value to the table, figure, or data listing.
- Outputs will be numbered in accordance with Synteract's SAS Programming Standards (WI-SOP-0205-001) and will follow the listed examples: t14.3.4.x-vs-<yyyy-mm-dd>.rtf, 116.2.4.x-mh-<yyyy-mm-dd>.rtf, and f14.x.x-ttdis-<yyyy-mm-dd>.rtf.

Tables

- Formal organization of tabulations may be changed during programming, if appropriate, eg, tables for the different variables may be combined into a single table, or tables with more than 1 variable may be split into several tables.
- Means and medians will be presented to 1 more decimal place than the raw data. SDs will be presented to 2 more decimal places than the raw data. Minimums and maximums will be reported with the same number of decimal places as the raw data.
- Percentages will be presented to the tenths place.
- For frequency counts of categorical variables, categories whose counts are zero will be displayed for the sake of completeness. For example, if none of the subjects discontinue due to "lost to follow-up," this reason will be included in the table with a count of 0. Categories with zero counts will not have zero percentages displayed.
- Lower and upper CI values must be presented to 1 decimal place more than the raw/derived data (ie, to the same number of decimal places as the mean).
- Percentiles (eg, 25%, 75%) must be presented to 1 decimal place more than the raw/derived data.
- For all inferential analyses, *P* values will be rounded to 4 decimal places (or at the highest level of precision) with a leading zero (0.0001). *P* values less than 0.0001 will be presented as "<0.0001."
- The last footnotes will be
 - "Source: xxx", where xxx indicates the source **table number(s)** if applicable (in case aggregated results like mean or median are plotted) or the source listing(s) (in case individual responses are plotted) and/or source dataset(s) (eg, ADaM).
 - "PROGRAM SOURCE: ...\\xx.sas, DATA CUT OFF DATE: DDMMYYYY, RUN DATE: DDMMYY hh:mm".
where extract date is the datestamp of the data snapshot used.

Pelle-926-301 Statistical Analysis Plan

17 June 2020

Figures

- Legends will be used for all figures with more than 1 variable or item displayed. Treatment group sizes (n=xx) will be included, as appropriate.
- Figures will be in black and white but can be in color to add value to the clarity and readability of a figure. Lines must be wide enough to see the line after being copied.
- The last footnotes will be
 - “Source: xxx”, where xxx indicates the source listing number(s) and/or source dataset(s) (eg, ADaM).
 - “PROGRAM SOURCE: ...\\xx.sas, DATA CUT OFF DATE: DDMMYYYY, RUN DATE: DDMMYY hh:mm”.where extract date is the datestamp of the data snapshot used.
- Line graphs over time of change from baseline results will include a horizontal dashed reference line at zero.
- For box plots, the horizontal line will represent the median, + represents the group mean, the length of the box represents the interquartile range (25th-75th percentiles), and the whiskers will represent the minimum and maximum.

Listings

- Formal organization of the listing may be changed during programming, if appropriate, eg, additional variables may be included, change in the column order, or the listing may be split into multiple parts due to space constraints.
- If not otherwise specified, all data listings will be sorted by treatment, center, subject number, visit, and date/time, as appropriate.
- All date values will be presented in a SAS date (eg, 29AUG2001) format showing actual dates entered and not imputed dates.
- All observed time values will be presented using a 24-hour clock HH:MM:SS format (eg, 01:35:45 or 11:26). Seconds will only be reported if they were measured as part of the study.
- The last footnote will be
 - “PROGRAM SOURCE: ...\\xx.sas, DATA CUT OFF DATE: DDMMYYYY, RUN DATE: DDMMYY hh:mm”.where extract date is the datestamp of the data snapshot used.

Missing or incomplete dates (ie, AEs (for determination of treatment-emergence only) and concomitant medications)

The most conservative approach will be systematically considered. If the AE onset date is missing/incomplete, it is assumed to have occurred during the study treatment phase (ie, considered a TEAE) except if the partial onset date or other data, such as the stop date, indicates differently. Similarly, a medication with partial start and stop dates could be considered as both a prior and concomitant treatment.

The following algorithms will be applied to missing and incomplete start and stop dates:

Start Dates

- If the day portion of the start date is missing, then the start date will be estimated to be equal to the date of first dose of study drug, provided the start month and year are the same as the first dose of study drug and the stop date is either after the first dose of study drug or completely missing. Otherwise, the missing day portion will be estimated as “01.”
- If both the day and month portions of the start date are missing, then the start date will be estimated to be equal to the date of first dose of study drug, provided the start year is the same as the first dose of study drug and the stop date is either after the first dose of study drug or completely missing. Otherwise, the event will be assumed to start on the first day of the given year (eg, ??-??-2013 is estimated as 01-JAN-2013).
- If the start date is completely missing and the stop date is either after the dose of study drug or completely missing, the start date will be estimated to be the day of study drug dosing. Otherwise, the start date will be estimated to be the first day of the same year as the stop date. All other non-AE and non-concomitant medication day calculations where only partial dates are available will be handled as follows: the first day of the month will be used in the calculations if the day part of a start date is missing while January 1 will be employed if both the month and day parts of a start date are missing.

Stop Dates

- If only the day of resolution is unknown, the day will be assumed to be the last of the month (eg, ??-JAN-2013 will be treated as 31-JAN-2013).
- If both the day and month of resolution are unknown, the event will be assumed to have ceased on the last day of the year (eg, ??-??-2013 will be treated as 31-DEC-2013).
- if the stop date is completely missing or the event is continuing, the event will be assumed to be after first dose of study drug and will be imputed using the last known date on the study.

Standard Calculations

Variables requiring calculation will be derived using the following formulas:

Days – A duration expressed in days between 1 date (date1) and another later date (date2) is calculated using the formulas noted below:

$$\text{duration in days} = \text{date2} - \text{date1} + 1$$

Months – A duration expressed in months is calculated using the INTCK function of SAS as follows:
months=intck('month','date1'd,date2'd, 'continuous').

Pelle-926-301 Statistical Analysis Plan

17 June 2020

Years – A duration expressed in years between 1 date (date1) and another later date (date2) is calculated as follows:

duration in years = intck('year',date1'd,date2'd, 'continuous').

Age – Age is calculated as the number of years from the date of birth (DOB) to the date of informed consent (DOIC). If the month of DOIC < month of DOB or the month of DOIC=DOB and the day of DOIC < day of DOB, then the following formula is used:

age (years) = year of DOIC – year of DOB – 1.

Otherwise, the following formula is used:

age (years) = year of DOIC – year of DOB.

Height – Height entries made in inches (in) are converted to centimeters (cm) using the following formula:

height (cm) = height (in) × 2.54.

Weight – Weight entries made in pounds (lb) are converted to kilograms (kg) using the following formula:

weight (kg) = weight (lb)/2.2046.

Body Mass Index (BMI) – BMI is calculated using height (cm) and weight (kg) using the following formula:

BMI (kg/m²) = weight (kg)/[[height (cm)/100]²].

Temperature – Temperature entries in degrees Fahrenheit are converted to degrees centigrade using the following formula:

temp (degrees centigrade) = 5/9 × [temp (degrees Fahrenheit) – 32].

Change from baseline – Change from baseline will be calculated as:

Change = postbaseline value – baseline value.

